**8.0 \* Explain how PHI will be acquired and used:**

Data will be collected by an investigator or research assistant. Sources of data include medical records and patient physical assessments/interviews conducted by study personnel. Data will be recorded and managed using REDCap electronic data capture tools hosted at the Clinical and Translational Science Center (CTSC) at Weill Cornell Medical College. REDCap (Research Electronic Data Capture) is a secure, web-based application designed to support data capture for research studies, providing: 1) an intuitive interface for validated data entry; 2) audit trails for tracking data manipulation and export procedures; 3) automated export procedures for seamless data downloads to common statistical packages; and 4) procedures for importing data from external sources.

Connection to REDCap occurs via the hospital's encrypted cable and wireless networks, and data will be entered through a password-protected computer terminal or iPad.

9.0

Explain how PHI will be protected during this study:

Print: 2014-018 - The Combination of Adductor Canal Block and Periarticular Injectio...

Page 33 of 37

<https://ecap.hss.edu/eCAP/ResourceAdministration/Project/PrintSmartForms?Project=cm.w...> 8/22/16

ID: 2014-018 Section: PART III - IRB Application - Assessment Procedures

Subject privacy and confidentiality will be maintained through the storage of study data in a password-protected computer database maintained by the PI and accessible only to the principal investigator, in addition to other IRB approved study personnel.

Each subject will be assigned a unique study number for identification in the study database. This unique study number will not be derived from or related to information about the individual. The key linking this unique study number to patient identifiers (i.e. name, medical record number, date of birth, registry number, etc...) will be maintained in a different password protected database maintained by to which only will have access.

.

**10.0 \* Justify your need to collect PHI on this study:**

PHI will be needed to screen for potential study participants, verify patient identity, and to coordinate patient information across multiple data sources, including ClinCIS, MMF, PS Reporter, REDCap, and paper charts. Some PHI including age, date of surgery, date of discharge and other unique identifying characteristics are essential data points for creating a demographic profile of

study participants.

[Help](#)

[Help](#)

## PHI Identifiers

1.0

Identify the types of PHI collected:

Name

- Questionnaires or Interviews

Billing Information or Databases

Mental Health Records

Data Registry

- Hospital or Medical Records

Biological Samples

DNA Samples

Other

1.1 If Other, please specify the type of PHI collected:

2.0

Select all the PHI Identifiers that apply:

Identifiers

Names

Print: 2014-018 - The Combination of Adductor Canal Block and Periarticular Injectio...

Page 34 of 37

<https://ecap.hss.edu/eCAP/ResourceAdministration/Project/PrintSmartForms?Project=cm.w...> 8/22/16

ID: 2014-018 Section: PART III - IRB Application - Assessment Procedures

Identifiers

Medical Record numbers

All elements of dates (except year) for dates related to an individual:

[Help](#)

## Data Safety Monitoring Plan

1.0 \* Check the one box below that most accurately reflects the

plan for data and safety monitoring for this study.

The study will be monitored only by the study investigators and/or sponsor.

1.1 If Other, Please specify your plan for data safety and monitoring for the study. If no DSMB required, Please specify why:

2.0 Describe the clinical criteria for withdrawing an individual subject from the study due to safety or toxicity concerns:

If a patient experiences complications, they will be kept at HSS for observation and withdrawn from the study. Such complications that would cause safety and toxicity concerns include local anesthetic toxicity, cardiac toxicity, and central nervous toxicity.

3.0 Summarize any pre-specified criteria for stopping or changing the study protocol due to safety concerns.

We do not have pre-specified criteria for stopping the study.

4.0 \* Are there any plans to perform an interim efficacy analysis:

No

4.1 If you answered Yes, please describe the plans to conduct an interim analysis.

N/A

[Help](#)

Final Page

You have completed your application!

Please hit "Continue" to finish the HSS Clinical Trial Form.

Please note that a submission may only be forwarded to the IRB by the Principal Investigator. To do this, the Principal Investigator must press the "SUBMIT STUDY" button in My Activities for this Study ID:2014-018.

Print: 2014-018 - The Combination of Adductor Canal Block and Periarticular Injectio...

Page 35 of 37

<https://ecap.hss.edu/eCAP/ResourceAdministration/Project/PrintSmartForms?Project=cm.w...> 8/22/16

ID: 2014-018 Section: PART III - IRB Application - Assessment Procedures

You can track the ongoing status of your submission by logging into the study workspace.

Please feel free to contact the IRB with any questions or concerns.

ID: 2014-018 Section: HSS Clinical Trial Registry

[Help](#)

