A spinal anesthetic with 0.5% bupivacaine (10 or 12.5) will be performed. Then the adductor canal block\* technique will be performed; supine position, after IV sedation. Ultrasound guided with linear transducer 8 MHz. Chiba needle, 22 G / 4 inches. The femoral artery will be identified in the adductor canal deep to the Sartorius muscle. The block will consist of 15 cc of Bupivacaine 0.25% with 2 mg of Preservative free Dexamethasone. The local anesthetic will be delivered periarterial between 12 and 6 o'clock. The surgeon will perform the periarticular injections; one deep injection prior to cementation and then a second more superficial injection prior to closure. The deep injection will consist of bupivacaine 0.5% with epinephrine, 30cc; morphine, 8 mg/ml, 1 cc; methylprednisolone, 40 mg/ml, 1 ml; cefazolin, 500 mg in 10 ml; normal saline, 22cc. The superficial injection will be 20 ml 0.25% bupivacaine. Patients will not be given intravenous opioids or ketamine during the operation. Patients will be given 4 mg Ondansetron and 20 mg Famotidine.

\*The block function will be assessed and recorded by the Anesthesiologist postoperatively.

The assessment of the adductor canal block will be done in the

Recovery room after the resolution of the spinal anesthesia. We will use a alcohol swab to test the cold sensation first on the non operated leg and then on the operated one. The test will be performed at the level of the medial maleoli of

the tibia. If the patient has sensation or no sensation it will be recorded as Block NOT working or Block working, respectively. The same procedures will be followed for the peri-articular injection only group, so as to not unblind participating patients.

Postoperative:

Print: 2014-018 - The Combination of Adductor Canal Block and Periarticular Injectio...

Page 15 of 37

<https://ecap.hss.edu/eCAP/ResourceAdministration/Project/PrintSmartForms?Project=cm.w...> 8/22/16

ID: 2014-018 Section: PART II - Clinical Research Proposal - Interventions or Observations

Analgesia:

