## Sample Size and Data Analysis

Support estimates with evidence from the literature of prior studies and perform an appropriate sample size calculation.

Print: 2014-018 - The Combination of Adductor Canal Block and Periarticular Injectio...

Page 20 of 37

<https://ecap.hss.edu/eCAP/ResourceAdministration/Project/PrintSmartForms?Project=cm.w...> 8/22/16

ID: 2014-018 Section: PART II - Clinical Research Proposal - Sample Size & Data Analysis

For hypothesis testing (e.g., the calculation of p-values using statistical tests), you need to

estimate your available sample size and calculate the effect size that will be detectable using your proposed statistical analysis plan. This also applies to a case series where you

plan hypothesis testing.

1.0 If you have consulted with a statistician, please indicate their name:

[name]

2.0 Proposed sample size analysis, include the following:

- Student's t-test, ANOVA, chi-square, regression, etc;
- Alpha level;
- Beta or power level;
- Primary outcome variable estimate (mean +/-s.d. for continuous outcome, frequency/percentage for categorical variable);
- Number of groups being compared (use 1 for paired analysis within the same subjects);
- Effect size or change expected between groups;
- Resulting number per group

A previous trial at HSS found the standard deviation (SD) in time until ready for discharge (based on achievement of PCA, nausea, diet, urination, pain, surgical, medical, and PT criteria) for TKR patients receiving periarticular injections to be 0.83 days (YaDeau, 2013). This SD was considered to be a reasonable estimate of the variability in the time until patient is able to independently negotiate stairs within the periarticular injection alone group. A 0.5 day difference in mean time until patient is able to independently negotiate stairs between the periarticular injection alone and periarticular injection + ACB groups was determined to be clinically meaningful. With two-sided alpha set at 0.05, power at 0.8, and the addition of 10% more patients to account for potential protocol violations, the number of patients required for a two-sample t-test is 53 patients per group (106 patients total\*).

\*Our a priori sample size calculation assumed that 96 of 106 enrolled patients would adhere to trial protocol. However, ultimately only 92 out of 106 patients adhered to trial protocol. Therefore, we plan to continue enrollment up to 114

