patients until 96 patients without protocol deviations are enrolled.

3.0

**Data Analysis:** describe how the primary outcome will be analyzed and what types of statistical calculations will be used. Do the same for each secondary outcome. Reiterate briefly the main analysis to be done, which groups, which variables, possible confounders. Address how possible confounders will be identified and handled in analysis:

Print: 2014-018 - The Combination of Adductor Canal Block and Periarticular Injectio...

Page 21 of 37

<https://ecap.hss.edu/eCAP/ResourceAdministration/Project/PrintSmartForms?Project=cm.w...> 8/22/16

ID: 2014-018 Section: PART II - Clinical Research Proposal - Sample Size & Data Analysis

The primary outcome, time until the patient is able to independently negotiate stairs, will be compared between the periarticular injection alone and periarticular injection + ACB groups with a two-sample t-test or Wilcoxon rank-sum test, depending upon the distribution of the data. The precision of the estimate of the difference between groups will either be reported as a 95% confidence interval for the difference in means or the Hodges-Lehmann estimate of location shift. Longitudinal secondary outcome data (NRS pain scores, narcotic consumption, incidence of side effects, painOUT score, and patient satisfaction) will be compared between groups via the generalized estimating equations (GEE) approach.

Change in KSS, and hospital length of stay will be compared between groups with two-sample t-tests or Wilcoxon rank-sum tests, depending upon the distribution of the data.

The success of blinding in each arm will be assessed with the Bang Blinding Index' (Bang H, Flaherty SP, Kolahi J, Park J. Blinding assessment in clinical trials: A review of statistical methods and a proposal of blinding assessment protocol. *Clin Res Regul Aff* 2010; 27:42-51.)

[Help](#)

[Help](#)

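### Withdrawing patients from the study because of complications may drop treatment-related poor outcomes from the efficacy comparison and leave toxicity unreported by arm

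*Combined protocol and SAP*

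**What the plan says.** The rule stands in the Data Safety Monitoring Plan, item 2.0: "If a patient experiences complications, they will be kept at HSS for observation and withdrawn from the study". The next sentence gives examples: "Such complications that would cause safety and toxicity concerns include local anesthetic toxicity, cardiac toxicity, and central nervous toxicity". The list is introduced as an inclusion, so it is not closed. The same section leaves monitoring to the investigators and/or sponsor and sets no stopping criteria.

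The other relevant places are these:

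- **Interventions and Observations, 1.0.** Both arms receive a deep and a superficial periarticular injection containing bupivacaine. The block arm also receives the block: "The block will consist of 15 cc of Bupivacaine 0.25% with 2 mg of Preservative free Dexamethasone". All are single administrations around the operation. The accelerated physical therapy regimen continues after surgery in both arms.
- **Specific Aims, 4.0 and 5.0.** The primary outcome is the time to independent stair negotiation. Length of stay and opioid use are secondary outcomes taken from hospital records. The listed side effects are nausea, dizziness, vomiting and pruritus; toxicity is not among them. It is not an item under Data Collection, 1.0 either.
- **Sample Size and Data Analysis, 2.0 and 3.0.** Enrolment may go up to 114 "patients until 96 patients without protocol deviations are enrolled". The analysis text names a t-test or rank-sum test, but no analysis population and no handling of missing data.
- **HSS Clinical Trial, 6.0.** The lay summary describes the same 96 as patients whose data can be used.

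**The concern.** This is an exclusion rule that acts after randomisation and is triggered by a possible effect of the study treatment. The trigger is plausibly linked to the outcome as well: a patient held for observation is likely to clear the stairs later and stay longer. If such patients drop out of the analysis, the arm with more complications looks faster than it was.

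Safety is also at stake. With toxicity neither an outcome nor a listed data item, and with patients leaving the study when it occurs, the plan has no stated route by which toxicity would be counted and compared between arms.

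The anesthesiologist knows the allocation (Randomization, 1.0 and 2.0; Consent Information, 1.0), and the documents do not say who decides that a complication calls for withdrawal.

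**Working it through.** **1. The plan's own sample size.** Inputs from Sample Size and Data Analysis, 2.0: difference 0.5 day, SD 0.83 day, two-sided alpha 0.05, power 0.80, 10% allowance.

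- Normal approximation: 2 × (0.83 × (1.960 + 0.842) / 0.5)² = 43.3, so 44 per arm. The exact t-test gives 45.
- With the allowance: 45 / 0.9 = 50 per arm. The plan states: "the number of patients required for a two-sample t-test is 53 patients per group".
- A rank-sum adjustment gives 45 / (3/π) = 47.1, so 48 per arm (96 in total), and 48 × 1.1 = 52.8, so 53. Both of the plan's figures fit this adjustment, which the text does not mention. That is a labelling gap, and the present point does not depend on it.

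**2. Exposure by arm (spinal excluded).** From Interventions and Observations, 1.0:

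- Both arms: 30 ml × 5 mg/ml + 20 ml × 2.5 mg/ml = 150 + 50 = 200 mg.
- Block arm adds 15 ml × 2.5 mg/ml = 37.5 mg, for 237.5 mg, which is 18.75% more.
- If the spinal figure of 10 or 12.5, printed without a unit, is read as mg, the excess is 37.5/210 to 37.5/212.5, about 18%.

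**3. Possible shift in the primary mean.** Suppose k of the N patients in one arm are left out, each D days slower than the rest. That arm's mean then falls by k × D / N. The documents give neither k nor D; the values below are assumptions.

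| N per arm | k = 1, D = 2 | k = 3, D = 3 |
|---|---|---|
| 48 | 2/48 = 0.042 day (8% of 0.5) | 9/48 = 0.188 day (38%) |
| 57 | 2/57 = 0.035 day (7%) | 9/57 = 0.158 day (32%) |

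**4. Would the loss be uneven?** Assume independent binomial counts with 57 per arm. Let risk rise in proportion to dose (risk ratio 237.5/200 = 1.19) or, as a harsher case, double. The control rates are assumed.

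| Control rate | Any event (RR 1.19) | Unequal counts (RR 1.19) | More in block arm (RR 1.19) | More in block arm (RR 2) |
|---|---|---|---|---|
| 0.1% | 0.12 | 0.11 | 0.06 | 0.10 |
| 0.5% | 0.47 | 0.41 | 0.23 | 0.35 |
| 1% | 0.72 | 0.59 | 0.33 | 0.50 |
| 2% | 0.92 | 0.73 | 0.42 | 0.63 |
| 5% | 1.00 | 0.84 | 0.51 | 0.80 |

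Imbalance towards the block arm is possible. Whether it is likely depends on rates that the documents do not give.

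**5. Does keeping everyone cost power?** Exact t-test power at 0.5 day and SD 0.83 is 0.832 with 48 per arm and 0.890 with 57, assuming equal arms and unchanged SD and effect. Nominal power is not lost.

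**The case against.** The strongest case on the other side has five parts.

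- **Withdrawal has a clinical function.** A reader might infer that it stops no study treatment at all. The documents do not support that: the accelerated therapy is tied to study participation and could end on withdrawal. This stands, but that regimen is common to both arms, and changing a patient's care does not require ending follow-up.
- **The text is silent on data.** A reader might infer that a withdrawn patient's data are deleted. No sentence says so, and length of stay, opioid use and the Knee Society Score come from hospital records or the registry. This stands; the supportable claim is that outcomes may be lost.
- **Replacement is not stated.** A reader might infer that withdrawn patients are replaced until 96 is reached. No passage classes a complication as a protocol deviation, and none of the 14 non-adherent patients (106 − 92) is attributed to toxicity. This stands too, although the wording of the target leaves replacement open.
- **The illustration uses chosen inputs.** One to three of 48 is 2% to 6% in one arm with none in the other, and a delay of 2 to 3 days is 2.4 to 3.6 planning SDs. A shift in means also does not carry over directly to a rank-sum test, which the plan allows. Both are fair limits.
- **It comes late.** With 106 of at most 114 patients enrolled, new wording governs follow-up of about 8 more. That is true, but the analysis rule covers everyone randomised.

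None of this supplies an analysis population, a data-retention rule or a toxicity outcome.

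**Conclusion.** The point holds as a gap that should be closed. A current rule takes randomised patients out of the study for a possible treatment effect, and nothing else in the plan says that they are followed, analysed or counted. Following the plan as written can therefore bias the stair-time comparison and lose toxicity information by arm.

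The size is uncertain. Under the assumed 1 to 3 one-sided exclusions with delays of 2 to 3 days, the shift is about 0.04 to 0.19 day with 48 per arm, or 0.035 to 0.16 with 57. If such events are rare, the efficacy bias is small and the loss of safety information is the main concern.

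A reader might infer that the loss most likely falls more heavily on the block arm. The extra 37.5 mg makes that plausible, but both arms receive 200 mg periarticularly. At assumed control rates of 0.5% or less and a risk ratio of 1.19, unequal counts of any kind are less likely than not. Nor do the documents show that any patient has been withdrawn under this rule.

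**What to change.** In the Data Safety Monitoring Plan, item 2.0, separate clinical management from study follow-up. State that patients with complications are managed as clinically needed and stay in study follow-up unless they withdraw consent. Then add to Sample Size and Data Analysis, 3.0:

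- their stair time, length of stay, opioid use, side effects and Knee Society Score are kept;
- they are analysed in the assigned arm in the primary analysis, with a stated rule for anyone who never reaches the stair criterion;
- complications, including the named toxicities, are reported by arm;
- a complication alone does not make a patient's data unusable, and such patients are not replaced toward the 96.

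Apply the same to any patient already withdrawn under the rule, using hospital records and the registry where consent allows.

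The cost is a few sentences and an amendment. The plan already has stair clearance assessed daily at the standard therapy visit after postoperative day 2, takes length of stay and opioid use from hospital records, and obtains the Knee Society Score at about 6 weeks through the registry. The added work is a toxicity field on the data sheet and recovery of records for any patient already withdrawn. No dose or clinical rule changes.

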## HSS Clinical Trial

The Clinical Trial Registry is posted on the HSS main page to highlight research (including retrospective studies) being conducted at HSS. This same language, once approved by the IRB, can then be used on flyers if you so choose, to post in an effort to recruit subjects.

1.0 Title: The Combination of Adductor Canal Block and Periarticular Injection with an Accelerated Rehabilitation Protocol. A novel technique for Patients Undergoing Total Knee Replacement (ACB PAI)

2.0 PI: [[name].](#)

3.0 Co-Investigators:

First Name Middle Name Last Name Title

[name], PhD IRB Vice Chair

[name] Research Assistant

[name]

[name]

[name] Volunteer

[name]

[name] Physical Therapist

[name]

[name]

[name]. MD

[name]

[name]

[name]

[name] Assistant Director, Research

[name]

[name] Physical Therapist

[name] Research Associate

[name]

[name]

[name]

[name]

[name] Regional Anesthesia fellow

4.0

Posting date:

Print: 2014-018 - The Combination of Adductor Canal Block and Periarticular Injectio...

Page 36 of 37

<https://ecap.hss.edu/eCAP/ResourceAdministration/Project/PrintSmartForms?Project=comb...> 8/22/16

ID: 2014-018 Section: HSS Clinical Trial Registry

Name

Upon IRB approval

Post on this date:

5.0

Condition:

Arthroplasty

Other:

6.0 State the summary including number of patients, enrollment period and duration of follow-up (use lay terms):

We plan to enroll up to 114 patients undergoing knee replacement in order to get 96 patients with usable data. All patients will receive peri articular injections as an anesthetic regimen. Half will additionally receive an adductor canal block.

Patients will also have an accelerated physical therapy protocol to aid the achievement of rehab milestones. The primary outcome is time when patient is able to meet physical therapy discharge criteria, indicated by the ability to independently negotiate stairs- non-reciprocal (one leg at a time), with or without rails, and with or without assistive device (walker or cane).

7.0 State the inclusion and exclusion criteria (use lay terms):

8.0 State the contact information for the study:

[Help](#)

Print: 2014-018 - The Combination of Adductor Canal Block and Periarticular Injectio...

Page 37 of 37

<https://ecap.hss.edu/eCAP/ResourceAdministration/Project/PrintSmartForms?Project=comb...>

8/22/16
